## **10.0 Statistical Considerations**

**Preliminaries.** This is a single-arm feasibility trial of Id Specific vaccinated DLI for treatment of multiple myeloma patients post allograft from a matched sibling donor who are not in CR or relapsing after transplant at least 3 months after stem cell transplant. The last myeloma therapy must be at least 3 weeks prior to entry. Labeling time of DLI as week 0, each donor will be vaccinated at weeks -8, -6, -2 and each patient will be vaccinated at weeks, 0, 4, and 8. Toxicity (TOX) will be defined as the event that the patient suffers grade 2, 3 or 4 GVHD or death within 6 months post DLI. The historical rate of TOX is 50% (54/107). The primary aim is to determine whether transfer of myeloma specific immunity is enhanced by vaccinating donors prior to donor lymphocyte infusion with an id-specific vaccine.

**Trial Conduct.** A maximum of 10 patients will be treated.

**Analysis of Myeloma Specific CTLs over time.** A generalized linear mixed model (Diggle, et al., 1998) will be fit to the longitudinal measurements of myeloma specific CTLs. For patient  $j = 1, \dots, 20$  at observation time  $t = -8, -6, -2, 0, 4, 8, 12$ , denote the myeloma specific CTL count by  $Y_{j,t}$  and covariate vector by  $Z_j$ . The model is given by

$$g\{E(Y_{j,t})\} = m + f_j(t) + b Z_j + \text{error}$$

where  $g$  is a suitable link function,  $m$  is the overall mean,  $f_j$  is a patient-specific function of  $t =$  time from day of DLI, accounting for the manner in which  $Y$  varies over time and includes a patient effect to account for correlation among the successive observations on each patient,  $Z_j$  is a component accounting for patient covariates with  $b$  is a covariate parameter vector, and "error" is the usual measurement of error.

Additional analyses of the final data will include analysis of survival times as functions of the treatments and patient prognostic covariates using an appropriate survival regression model determined by goodness-of-fit analyses.

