**Toxicity Monitoring Rule.** For the purpose of safety monitoring, "toxicity" will be defined as Grade 2-4 acute GVHD within 6 months of DLI. Based on an historical toxicity rate of 50%, denoting  $q = \text{Pr}(\text{toxicity})$ , it will be assumed that  $q$  follows a beta(.50, .50) prior. The trial will be stopped early for safety if  $\text{Pr}(Q > .50 | \text{data}) > .90$ . This rule will stop the trial early if  $[\# \text{ toxicities}] / [\# \text{ patients}]$  is greater than or equal to 2/2, 3/3, 4/4, 5/6, 6/7, or 7/9. The operating characteristics of this rule are as follows:

True Pr(Toxicity)	Pr(Stop Early)	Median Sample Size
.50	.35	10
.60	.52	8
.70	.70	5
.80	.88	2

**PROTOCOL COMPLIANCE** Patients will be reviewed by the study investigators who will score the patient for toxicity, and GVHD. Data must be entered in PDMS and the Study Chairman will be the final arbiter of toxicity and other outcomes should a difference of opinion exist.

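### The stopping-rule table assumes six-month outcomes are known at once, and the plan does not say how patients still inside the window are counted, so the printed figures are not assured

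*Combined protocol and SAP*

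**What the plan says.** All of this is in Section 10.0 unless noted. For the monitoring rule, toxicity "will be defined as Grade 2-4 acute GVHD within 6 months of DLI". (The Preliminaries paragraph of the same section defines TOX more widely, adding death; the monitoring definition is used here.) The toxicity probability "follows a beta(.50, .50) prior". "The trial will be stopped early for safety if" the posterior probability that it exceeds .50 is above .90. This is then restated as a list: stop if toxicities over patients "is greater than or equal to 2/2, 3/3, 4/4, 5/6, 6/7, or 7/9". A table follows, introduced by "The operating characteristics of this rule are as follows", giving stopping probabilities of .35, .52, .70 and .88 and medians of 10, 8, 5 and 2 at true rates of .50, .60, .70 and .80.

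On conduct, the section says only that "A maximum of 10 patients will be treated". The supplied text gives no accrual rate, no interval between infusions, no pause while outcomes are pending, and no statement of which patients enter the denominator. Some front matter is not in the supplied text.

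Sections 7.0 B and D schedule GVHD assessments before the infusion, before each vaccine (weeks 0, 4 and 8), and then 3 and 6 months after the last vaccine. The last two fall roughly 5 and 8 months after infusion, so no scheduled visit closes the six-month window.

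**The concern.** The rule compares a running count of toxicities with a running count of patients, starting at two. A toxicity is known when it occurs, but its absence is known only after six months. If infusions come faster than that, several patients are pending at each look, and the text allows at least three counts:

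- All treated patients. Pending patients then act as non-toxic and the rule is diluted.
- Only patients who have completed six months. The counts are unbiased, but more patients have been treated by the time the boundary is reached.
- Only known outcomes. Toxicities enter before non-toxicities and the rule stops too readily.

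This is the trial's only quantitative safety rule; Section 9.0 otherwise relies on the study chair's judgement about toxicity. Two people applying the same text to the same data could reach opposite decisions, and the table tells neither of them what protection to expect.

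**Working it through.** **Inputs (Section 10.0).** Beta(.5, .5) prior, reference rate .50, posterior cut-off .90, maximum of 10 patients, six-month window. Stopping early means fewer than 10 treated.

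**Step 1: reproduce the table with immediate outcomes.** The posterior criterion gives the boundary 2/2, 3/3, 4/4, 4/5, 5/6, 6/7, 6/8, 7/9. With a look after every patient, a first crossing is possible only at n = 2, 5 or 8. With true rate p:

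Pr(stop early) = p² + 2p⁴(1−p) + 7p⁶(1−p)²

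- p = .50: .250 + .0625 + .0273 = .340
- p = .60: .360 + .1037 + .0523 = .516
- p = .70: .490 + .1441 + .0741 = .708
- p = .80: .640 + .1638 + .0734 = .877

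The running sum first reaches one half at n = 8, 5 and 2 for p = .60, .70 and .80, and never does for .50. The medians are therefore 10, 8, 5 and 2. The probabilities agree with print to about one point and all four medians match, so the table is the immediate-outcome calculation.

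**Step 2: check the printed count list.** It has no entry for n = 5 or n = 8, although the posterior is .912 at 4/5 and .923 at 6/8, both above .90. Taken literally, the list can first be crossed only at n = 2, 6 or 9:

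Pr(stop early) = p² + 2p⁵(1−p) + 9p⁷(1−p)²

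This gives .299, .463, .658 and .847, with medians 10, 10, 6 and 2. The table therefore belongs to the criterion and not to the list. The steps below use the criterion.

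**Step 3: delay, counting completed windows only (exact).** If infusions are g months apart, then L = ceil(6/g) − 1 further patients have been treated by the time the nth window closes. A crossing at n stops the trial early only if n + L < 10.

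- g = 3, L = 1: crossings at 2, 5 and 8 all still count. Probabilities are unchanged; medians are 10, 9, 6 and 3.
- g = 2, L = 2: the crossing at 8 is lost. Probabilities are .31, .46, .63 and .80; medians are 10, 10, 7 and 4.
- g = 1, L = 5: only the crossing at 2 remains, so the probability is p²: .25, .36, .49 and .64. Medians are 10, 10, 10 and 7.

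**Step 4: delay under all three counts (simulation, monthly infusions).** Accrual and onset are assumptions, since the documents give neither. The completed-window column is the exact p²; simulation of those cells gave .25 to .27 and .64 to .65.

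| Onset | True rate | All treated | Completed windows | Known outcomes | Print |
|---|---|---|---|---|---|
| Uniform, 6 months | .50 | .04 | .25 | .66 | .35 |
| Uniform, 6 months | .80 | .29 | .64 | .96 | .88 |
| Uniform, 3 months | .50 | .17 | .25 | .82 | .35 |
| Uniform, 3 months | .80 | .72 | .64 | .99 | .88 |

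At .80 with six-month onset the medians are 10, 7 and 5, against 2 in print. The known-outcomes column applies the rule each time an outcome becomes known. Looking only just before each infusion lowers it, but at .50 it stays well above print.

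**Step 5: three-month spacing.** Across the three counts and both onset patterns, the stopping probability is about .27 to .43 at .50 and .82 to .91 at .80, with a median of 2 to 5 at .80.

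**The case against.** The strongest reply is that accrual may well be slow. The trial treats at most ten patients, each vaccine is patient-specific, donors are vaccinated over eight weeks before collection, and recipients are restricted by immunoglobulin subclass and by having a compatible related donor. Counting completed windows only is a natural reading, and under it three-month spacing leaves every stopping probability unchanged.

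The dilution figures also depend on assumed onset. With all treated patients counted and onset uniform over two months, two-month spacing gives about .34 at .50 and .88 at .80 with a median of 2, essentially the printed table. Monthly spacing gives about .27 and .83 with a median of 4.

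Much of this stands. A reader might infer that the figures hold only if every outcome is known before the next infusion, so that ten patients would need at least 9 × 6 = 54 months. Step 3 shows that this is not so for the stopping probabilities. A reader might also infer that the rule necessarily becomes weaker, but the direction depends on the count used.

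The reply does not close the gap. The supplied text neither states nor requires slow accrual, and it does not choose a count. Earlier onset, which helps when all treated patients are counted, worsens over-stopping when only known outcomes are: at .50 with monthly spacing, to about .83 to .87 for onset within two to three months.

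**Conclusion.** The point holds in this form: the table is the immediate-outcome calculation, the event takes up to six months, and the rule's denominator is undefined, so the printed operating characteristics are not assured. With monthly infusions the chance of stopping could lie anywhere from .04 to .82 at a true rate of .50, and from .29 to .99 at .80, over the three counts and the two onset patterns tabulated. At three-month spacing the departure is small.

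A reader might go further and conclude that the design fails to deliver its stated protection under normal recruitment. The documents do not support that, because they give no accrual rate or onset distribution, and plausible slow accrual keeps the probabilities near print.

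The mismatch between the count list and the posterior criterion needs no such assumption. It follows from the printed rule alone. The correction should be made, but the point does not undermine the trial as a whole.

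**What to change.** In Section 10.0, define the patient count so that toxicities are not counted ahead of non-toxicities and pending patients are not counted as full non-toxicities. One option is observed toxicities plus toxicity-free patients, each weighted by the fraction of six months observed. State the expected spacing of infusions.

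Replace the table with operating characteristics simulated under that definition, for spacings of 1, 2, 3 and 6 months and for both early and uniform onset. In the same run, reconcile the count list with the posterior criterion at 4/5 and 6/8, so that list, criterion and table describe one rule.

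The cost is a sentence or two and a re-run table; no extra patients, visits or accrual hold are needed to correct the stated figures. The figures may become less favourable. Weighting does not restore the printed values at fast accrual: with onset uniform over six months, simulation gave about .66, .80 and .85 at a true rate of .80 (medians 8, 5 and 4), and .16, .25 and .27 at .50, for spacings of 1, 2 and 3 months.
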